## Hypoglycaemic episodes

### *Classification of Hypoglycaemia:*

Treatment emergent: hypoglycaemic episodes will be defined as treatment emergent if the onset of the episode occurs on or after the first day of trial product administration, and no later than 1 day after the date of last contact.

Nocturnal hypoglycaemic episodes: are episodes occurring between 00:01 and 05.59 both inclusive.

[figure not shown]
Hypoglycaemic episodes are classified according to the Novo Nordisk classification of hypoglycaemia (see [Figure 2-1](#)) and the ADA classification of hypoglycaemia (see [Figure 2-2](#)).

### *Novo Nordisk classification of hypoglycaemia*

In normal physiology, symptoms of hypoglycaemia occur below a plasma glucose level of 3.1 mmol/l (56 mg/dl). Therefore, Novo Nordisk has included hypoglycaemia with plasma glucose levels below this cut-off point in the definition of blood glucose (BG) confirmed hypoglycaemia.

Novo Nordisk uses the following classification (see [Figure 2-1](#)) in addition to the ADA classification:

- Severe hypoglycaemia according to the ADA classification
- Symptomatic BG confirmed hypoglycaemia: An episode that is BG confirmed by plasma glucose value <3.1 mmol/l (56 mg/dl) **with** symptoms consistent with hypoglycaemia.
- Asymptomatic BG confirmed hypoglycaemia: An episode that is BG confirmed by plasma glucose value <3.1 mmol/l (56 mg/dl) **without** symptoms consistent with hypoglycaemia.
- Severe or BG confirmed symptomatic hypoglycaemia: An episode that is severe according to the ADA classification or BG confirmed by a plasma glucose value <3.1 mmol/l (56 mg/dl) **with** symptoms consistent with hypoglycaemia.
- BG confirmed hypoglycaemia: An episode that is BG confirmed by a plasma glucose value <3.1 mmol/l (56 mg/dl) **with** or **without** symptoms consistent with hypoglycaemia.
- Severe or BG confirmed hypoglycaemia: An episode that is severe according to the ADA classification or BG confirmed by a plasma glucose value <3.1 mmol/l (56 mg/dl) **with** or **without** symptoms consistent with hypoglycaemia.

[figure not shown]

Note: Glucose measurements are performed with capillary blood calibrated to plasma equivalent glucose values

**Figure 2–1 Novo Nordisk classification of hypoglycaemia**

### *ADA classification of hypoglycaemia*

- Severe hypoglycaemia: An episode requiring assistance of another person to actively administer carbohydrate, glucagon, or take other corrective actions. Plasma glucose concentrations may not be available during an event, but neurological recovery following the return of plasma glucose to normal is considered sufficient evidence that the event was induced by a low plasma glucose concentration.
- Asymptomatic hypoglycaemia: An episode not accompanied by typical symptoms of hypoglycaemia, but with a measured plasma glucose concentration  $\leq 3.9$  mmol/l (70 mg/dl).
- Documented symptomatic hypoglycaemia: An episode during which typical symptoms of hypoglycaemia are accompanied by a measured plasma glucose concentration  $\leq 3.9$  mmol/l (70 mg/dl).
- Pseudo-hypoglycaemia: An episode during which the person with diabetes reports any of the typical symptoms of hypoglycaemia with a measured plasma glucose concentration  $> 3.9$  mmol/l (70 mg/dl) but approaching that level.
- Probable symptomatic hypoglycaemia: An episode during which symptoms of hypoglycaemia are not accompanied by a plasma glucose determination but that was presumably caused by a plasma glucose concentration  $\leq 3.9$  mmol/l (70 mg/dl).

Note: Glucose measurements are performed with capillary blood calibrated to plasma equivalent glucose values

**Figure 2–2 ADA classification of hypoglycaemia**

### *Analysis of hypoglycaemic episodes*

The number of treatment emergent hypoglycaemic episodes will be summarised by treatment. Separate summaries will be made for the Novo Nordisk and for the ADA classifications and for nocturnal episodes. The summaries will be made for the treatment period, for the observation period and for the entire trial period.

The total number of treatment emergent severe or BG confirmed symptomatic hypoglycaemic episodes will be analysed using a negative binominal regression model with a log link function, and the logarithm of the exposure time as an offset. The model will include treatment, stratum and sex as factors and age as a covariate. The treatment ratio will be estimated and the corresponding two-sided 95% CI will be calculated. The analysis will be made for the treatment period, for the observation period and for the entire trial period.

The total number of treatment emergent nocturnal severe or BG confirmed symptomatic hypoglycaemic episodes will be analysed using the same model as above. The analysis will be made for the treatment period, for the observation period and for the entire trial period.

To the extent that data allows, additional analyses may be performed for the other classes of hypoglycaemic episodes using the same model as described above.

Sensitivity analyses will be made (for each analysed class of hypoglycaemia) comparing number and individual rates of hypoglycaemic episodes, respectively, using the Wilcoxon-Mann-Whitney method. This will be made for all different pairs of treatments.

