# 8.3.3 4-point self-measured plasma glucose profiles

Subjects will be instructed to perform SMPG measurements before breakfast, before lunch, before dinner and at bedtime daily to allow optimal insulin titration. The plasma glucose levels, the date and the time point of all measurements will be recorded for each time point stated in the e-diary.

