  - Neuroglycopenic: confusion, drowsiness, speech difficulty, visual disturbances, odd behaviour, impaired balance or incoordination

CONFIDENTIAL

Date: Version: Status: Page:

- General malaise: headache or malaise
- Did the subject experience other symptoms?

The Investigator must review the e-diary data for correct reporting of SMPGs and hypoglycaemic episodes at each contact. If the investigator experiences missing data in the diary, the subject must be questioned whether there have been any severe hypoglycaemic episodes since the last visit i.e. any hypoglycaemic episodes where the subject was not able to self-treat. Any severe hypoglycaemic episodes must be reported on a hypoglycaemic episode form.

Non-severe hypoglycaemic episodes not having a hypoglycaemic episode form completed within 7 days since the SMPG measurement will not be reported retrospectively and missing data points for non-severe hypoglycaemic episodes will generally not be questioned by the investigator or queried by Novo Nordisk due to subject's short recall of non-severe hypoglycaemic episodes  $\frac{35,36}{2}$ .

The subject must be re-trained in how to report hypoglycaemic episodes if the investigator identifies unreported hypoglycaemic episodes.

If the hypoglycaemic episode fulfils the criteria for an SAE and/or a medical event of special interest (MESI) then an AE form and a safety information form must also be filled in, see section 12.1.

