## 2.10 Section 8.7 Subject compliance

Throughout the trial, the investigator will remind the subjects to follow the trial procedures and requirements to ensure subject compliance. If a subject is found to be non-compliant, the investigator will remind the subject of the importance of following the instructions given including taking the trial products as prescribed. Substantial failure to comply with the prescribed dose regimen can lead to withdrawal at the discretion of the investigator.

In case of subject non-compliance with data entry in the eDiary, re-training should be performed and documented.

Protocol Amendment no 6 Trial ID: NN9828-4150

CONFIDENTIAL

Date: Version: Status: Page: 17 October 2017 Novo Nordisk 1.0 Final 1 of 3

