## 2.1 Sample size calculation

This is a phase 2 trial and the first Novo Nordisk trial of NNC0114-0006 in subjects with newly diagnosed T1DM. Therefore the knowledge on treatment effects and on the standard deviation of the primary endpoint is limited.

The statistical power calculations have been done under the following assumptions

- The primary endpoint is  $AUC_{0-4h}$  for a MMTT stimulated C-peptide concentration-time curve at week 54 relative to baseline, i.e.  $AUC_{0-4h, C-peptide, 54w} / AUC_{0-4h, C-peptide, baseline}$ . The primary endpoint will be log-transformed in the statistical analysis and this will be denoted  $\ln(AUC_{0-4h, C-peptide, \Delta 54w})$ . Thus,  $AUC_{0-4h, C-peptide, \Delta 54w}$  is the proportion of  $AUC_{C-peptide}$  that is preserved after 54 weeks relative to the level at baseline. E.g. a reduction of  $AUC_{C-peptide}$  of 35% corresponds to a preservation of 65% and value of the  $\ln(AUC_{0-4h, C-peptide, \Delta 54w})$  is  $\ln(0.65) = -0.431$ .
- The residual standard deviation of  $\ln(AUC_{0-4h, C-peptide, \Delta 54w})$  in the model described above may depend on the treatment. Based on the results of Herold et al. the standard deviation is assumed to be 1 in the placebo group and 0.5 in the group treated with NNC0114-0006 in combination with liraglutide.
- The expected preservation in the placebo treated patients is 65%, based on the results of Herold et al. who found a mean of 70% decline in  $AUC_{C-peptide}$  over a 24-months period. Assuming a linear decline, the mean 12-months decline would be 35%, i.e. a preservation of 65%. The statistical power calculations have been done assuming three levels of treatment effects for NNC0114-0006 in combination with liraglutide; a preservation of 85% and 95% and 98%, respectively.

[Table 2-1](#) shows the statistical power for the test of no treatment effect if the true mean preservation is 85%, 95% or 98% in the group treated with NNC0114-0006 in combination with liraglutide and 65% in the placebo group when the numbers of completers are 40, 60 or 80, respectively using a two-sided test and 5% level of significance. The rows corresponding to the chosen number of (completing) subjects are highlighted.

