**Table 2–1 Power calculations**

True treatment effect (preservation)	N (completers per group)	Statistical power
85%	40	0.320
85%	60	0.451
85%	80	0.566
95%	40	0.561
95%	60	0.740
95%	80	0.854
98%	40	0.628
98%	60	0.804
98%	80	0.903

Assuming a preservation of 98% and a SD of 0.5 for NNC0114-0006 in combination with liraglutide and a preservation of 65% and a SD of 1 for placebo, then the power will be 80.4% with 60 subjects completing the trial in each of the two treatment arms.

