#### **Hyperglycaemic episodes**

Hyperglycaemic episodes will be defined as treatment emergent if the onset occurs on or after the first day of trial product administration.

The number of treatment emergent hyperglycaemic episodes will be summarised by treatment. The summaries will be made for the treatment period, for the observation period and for the entire trial period.

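### Hyperglycaemic episodes are reported as bare counts with no adjustment for follow-up, and the exposure time used for hypoglycaemia is neither defined nor checked against e-diary completeness

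*SAP*

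**What the plan says.** Subjects record both hypo- and hyperglycaemic episodes in an e-diary (Protocol 8.3.2 and 8.6.3). Glucose is to be self-measured every day: subjects are told to "perform SMPG measurements before breakfast, before lunch, before dinner and at bedtime daily to allow optimal insulin titration" (Protocol 8.3.3).

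For hypoglycaemia, SAP 2.4.1.2 fits a "negative binominal regression model with a log link function, and the logarithm of the exposure time as an offset" to severe or BG confirmed symptomatic episodes and to their nocturnal subset. It does so for the treatment period, the observation period and the whole trial. Exposure time is not defined. SAP Section 2 sets the periods by dates: first dose, Visit 63, and last visit or last contact. The same section of 2.4.1.2 also tabulates raw numbers of episodes and plans Wilcoxon-Mann-Whitney comparisons of both numbers and individual rates.

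For hyperglycaemia, SAP 2.4.1.2 says only: "The number of treatment emergent hyperglycaemic episodes will be summarised by treatment". The summaries cover the same three periods, with no model, rate or offset.

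On gaps in the diary, Protocol 8.4.2.7 does not accept a non-severe hypoglycaemic episode if its form is not completed within 7 days, and "missing data points for non-severe hypoglycaemic episodes will generally not be questioned by the investigator or queried by Novo Nordisk". Severe episodes are different. The investigator must ask about them when diary data are missing, and Amendment 2 allows late entry through a data change request. Confirmed DKA is reported as a serious adverse event in the eCRF (Protocol 8.4.2.6).

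**The concern.** A count without person-time mixes how often episodes happen with how long subjects were followed. Attrition is expected, so hyperglycaemia counts will be low, and the arms cannot be compared fairly if one of them loses more subjects or loses them earlier. The SAP solves this for hypoglycaemia and leaves it unsolved for hyperglycaemia, although the data source and the periods are the same.

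The second issue is what the hypoglycaemia offset measures. Period length is the natural reading, because the model is also applied to the observation period, when subjects are off drug and time on drug would make no sense. On that reading, a day with no diary entry adds exposure but can hardly add a non-severe event. The number of hypoglycaemic episodes to week 54 is one of the endpoints marked for public disclosure; hyperglycaemia is not. Nothing in the plan would show a reader how complete the diary was in each arm.

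**Working it through.** 1. **The plan's own figures.** The documents give no rate, sample size or power for either episode type. The nearest stated figure concerns the primary endpoint: "then the power will be 80.4% with 60 subjects completing the trial in each of the two treatment arms". On the log scale the effect is ln(0.98/0.65) = 0.4106 and the standard error is √((1² + 0.5²)/60) = 0.1443. A noncentral t calculation with Satterthwaite degrees of freedom gives 0.803, against the stated 0.804. This has no bearing on episodes, but it ties in the attrition allowance: 60/(240/304) = 76 per arm, and 304/4 = 76.

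2. **Attrition.** Protocol 6.1 plans 304 randomised and 240 reaching the primary endpoint. The loss is 64/304 = 21.05%.

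3. **Effect on counts.** Assume that a share d drops out, uniformly over 54 weeks, and that follow-up ends at dropout. Mean follow-up is 54 × (1 − d/2).
   - d = 0.2105: 54 × 0.8947 = 48.3 weeks, so counts are 10.5% low. With equal dropout the ratio between arms is still 1.00.
   - d = 0.30 against 0.12 (assumed; the average is 0.21): 0.85/0.94 = 0.904. Reversed, the ratio is 1.106.

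4. **What an offset does.** Negative binomial simulation: 76 per arm, 400 runs, true ratio 1, an assumed 5 episodes per year and dispersion 1. With 30% against 12% dropout the ratio is 0.908 without an offset and 1.002 with the log of follow-up as offset. The existing hypoglycaemia offset therefore removes the dropout effect.

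5. **Diary gaps under a period-length offset.** Let c be the share of days with diary recording. The recorded rate is the true rate × c, and the recorded ratio is the true ratio × c(active)/c(control). The values of c are assumptions. Dropout is 21% in both arms and the true ratio is 1.

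| Completeness, active / control | Closed form | Simulated, period offset | Rejected at 5% | Simulated, diary-day offset | Rejected at 5% |
|---|---|---|---|---|---|
| 80% / 80% | 1.00 | 1.000 | 7% | 1.001 | 7% |
| 80% / 95% | 0.842 | 0.847 | 17% | 1.007 | 6% |
| 70% / 90% | 0.778 | 0.784 | 23% | 1.011 | 6% |

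   At 80% in both arms the fitted control rate is 3.98 per year against a true 5, about 20% low. Other unequal pairs run from 0.60/0.90 = 0.67 to 0.95/0.80 = 1.19. The simulation loses every episode on a silent day, including severe ones that would in fact be asked about, so it overstates the loss to that extent. The diary-day offset works here because the simulated diary days are exactly the days on which episodes could be recorded.

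6. **A case where exposure may outrun the diary.** For a subject withdrawn before week 54, the treatment period runs to last contact (SAP Section 2). That may be Visit 90, 15 weeks after the last infusion (Protocol 8.1.7). Amendment 2 requires a withdrawn subject to return the e-diary without saying when; the flow chart lists its collection at Visits 89 and 90. If it is returned at withdrawal, assumed 6 weeks after a last infusion at week 6 to 36, the diary covers 12/21 = 57% to 42/51 = 82% of the period.

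**The case against.** The strongest reply is that the plan has safeguards and that every size above rests on assumed completeness. Sites are in contact with subjects at least weekly (Appendix A, Section 1), about the length of the 7-day window. The investigator reviews the diary at each contact and re-trains where unreported episodes are found (Protocol 8.4.2.7). The titration group reviews data within 24 hours on weekdays and may ask for missing entries (Appendix A, Section 5). The e-diary has edit checks (Protocol 13.3). The 7-day rule is stated for hypoglycaemia, not hyperglycaemia. All of this limits gaps and stands, but none of it measures how many gaps remain.

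A diary-day offset can also mislead. A recorded low is itself a diary entry. If subjects skip routine readings but still report symptomatic lows, the correction overshoots: 0.90/0.80 is up to +12.5%, and 0.90/0.70 up to +29%. A day with one of four readings counts as fully observed. This is a good reason to keep period length as the primary offset and use diary days only in a sensitivity analysis.

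A reader might infer four stronger points that the documents do not support:
- That the SAP specifies calendar time. It says exposure time; period length is an inference, though a strong one.
- That dropout biases the hypoglycaemia rate ratio. The offset adjusts for it (step 4). Dropout affects only the raw counts and the Wilcoxon comparison of numbers.
- That Amendment 5 shows actual non-compliance. It adds "In case of subject non-compliance with data entry in the eDiary, re-training should be performed and documented", but its rationale reports no observed problem.
- That the burden of pen injections would make recording differ by arm. The trial is double-dummy, so all arms inject daily and receive infusions.

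**Conclusion.** The point holds as a modest improvement. Hyperglycaemia lacks an exposure adjustment that the SAP already uses for hypoglycaemia. At the planned 21% attrition its counts are about 10.5% low if dropout is uniform, and a between-arm count ratio is distorted only if dropout differs (about 0.90 at an assumed 30% against 12%). No hyperglycaemia ratio or test is planned, so the harm lies in how the table will be read.

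For hypoglycaemia, if exposure time means period length, rates for non-severe episodes are understated in proportion to missing diary days. The treatment ratio is biased only if completeness differs by arm, and nothing in the documents shows that it does. Severe hypoglycaemia and confirmed DKA have other routes into the database. The missing definition alone would be a point of detail. What deserves a change is the bare hyperglycaemia count and the lack of any check on diary completeness.

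**What to change.** In SAP 2.4.1.2:
- Analyse hyperglycaemic episodes with the negative binomial model and covariates already given for hypoglycaemia, with log period length as offset, and report episodes per patient-year by arm.
- State that exposure time is the length of the relevant period as set out in SAP Section 2, and keep it as the primary offset for both episode types.
- Add a sensitivity analysis for both types, taking exposure as the number of days with at least one scheduled 4-point SMPG entry. Fix in advance a rule for subjects with no such day, since log(0) is undefined.
- Tabulate those days by arm and period.

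Scheduled SMPG entries are a better marker than insulin entries, because insulin may be paused or stopped (Protocol 5.3.3 as amended by Amendment 2).

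The cost is some extra analysis and the transfer of a daily SMPG-entry flag. SAP Section 3 notes that insulin doses are transferred from the e-diary only for the days before Visits 3, 63 and 89, so the flag needs its own transfer. The titration group's access is for surveillance and does not supply analysis data. The wording should be settled before the randomisation code is broken.

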#### Key secondary endpoints

- Number of treatment emergent episodes of diabetic ketoacidosis (DKA) from first dose of trial product to week 54
- Number of treatment emergent hypoglycaemic episodes according to the American Diabetes Association (ADA) and Novo Nordisk definitions from first dose of trial product to week 54
- AUC0-4h for MMTT stimulated C-peptide concentration time curve at week 80 relative to baseline
- AUC0-2h for MMTT stimulated C-peptide concentration time curve at week 54 and week 80 relative to baseline
- Maximum MMTT stimulated C-peptide concentration (Cmax, C-peptide) at week 54 and week 80 relative to baseline
- Change in fasting C-peptide from baseline to week 54 and week 80
- Change in HbA1c from baseline to week 54 and week 80
- Change in fasting plasma glucose from baseline to week 54 and week 80
- Total daily insulin dose in units per kg (three day average) at week 54 and week 80

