# 8.2.7 Diabetes treatment history

The following information has to be recorded:

- Start date of current diabetes treatment
- Number of severe hypoglycaemic episodes since diagnosis

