# 8.4.2.7 Hypoglycaemic episodes

Blood glucose should always be measured and recorded when a hypoglycaemic episode is suspected.

All plasma glucose values:

- $\leq 3.9 \text{ mmol/l} (70 \text{ mg/dl}) \text{ or}$
- > 3.9 mmol /l (70 mg/dl) occurring in conjunction with hypoglycaemic symptoms

should be reported according to the instructions below throughout the trial from visit 2 to visit 89. Upon onset of a hypoglycaemic episode the subject is recommended to measure blood glucose every 15 minutes in accordance to current guidelines  $\frac{33}{2}$ .

A SMPG  $\leq$ 3.9 mmol/l (70 mg/dl) or hypoglycaemic symptoms must trigger a hypoglycaemic episode form to be completed by the subject. Repeated SMPG measurements and/or symptoms will per default be considered as one hypoglycaemic episode until a succeeding measurement is >3.9 mmol/l (70 mg/dl) or symptoms have been resolved. One hypoglycaemic episode form is to cover these measurements and/or symptoms. However, each hypoglycaemic episode form will cover a period of maximum 60 minutes after onset of a hypoglycaemic episode.

In case of several low SMPG values within the 60 minute interval, the lowest value is the one that will be reported as the SMPG value for the hypoglycaemic episode but the start time of the episode will remain as the time for the first SMPG value and/or symptom.

If a new low SMPG value is measured or the subject still has symptoms more than 60 minutes after the first reported low SMPG value it is considered as a new episode and a new hypoglycaemic episode form is to be filled in.

The record should include the following information (layman-language will be used in the e-diary to phrase the respective questions ensuring that subjects understand the questions):

- Date and time of hypoglycaemic episode
- The plasma glucose level before treating the episode (if available) and any follow up measurements. (The lowest value measured during the hypoglycaemic episode will be reported as the SMPG value for the episode, the remaining values will be kept as source data).
- Whether the episode was symptomatic (Yes/No). (A hypoglycaemic episode starting as non-symptomatic should be updated to symptomatic if the subject experiences symptoms later during the episode. The subjects are therefore to be prompted whether there are changes to symptoms for each low SMPG value within the 60 minutes period).

Protocol		Date:	07 May 2015	Novo Nordisk
Trial ID: NN9828-4150	CONFIDENTIAL	Version:	2.0	

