#### 12.2 Reporting of adverse events

All events meeting the definition of an AE must be collected and reported. This includes events from the first trial-related activity after the subject has signed the informed consent until the end of the post-treatment follow-up period (26 weeks after the end of treatment). The events must be recorded in the applicable eCRF forms in a timely manner, see timelines below and Figure 12–1.

During each contact with the trial site staff, the subject must be asked about AEs and technical complaints, for example by asking: "Have you experienced any problems since the last contact?"

 $^2$  With the exception of hyperglycaemic and hypoglycamic episodes for which reporting starts at V2.

Protocol Trial ID: NN9828-4150 UTN: U1111-1154-7172	CONFIDENTIAL	Date: Version: Status:	07 May 2015 2.0 Final	Novo Nordisk
EudraCT no.: 2014-001215-39		Page:	91 of 141	

All AEs, either observed by the investigator or subject, must be reported by the investigator and evaluated. Novo Nordisk assessment of expectedness is performed according to the following reference documents:

- NN9211 IB, edition 3, 07 August 2013 and updates thereto
- NN9828 IB, edition 1, 2015 and updates thereto

All AEs must be recorded by the investigator on an AE form. The investigator should report the diagnosis, if available. If no diagnosis is available, the investigator should record each sign and symptom as individual AEs using separate AE forms.

For SAEs a safety information form must be completed in addition to the AE form. If several symptoms or diagnoses occur as part of the same clinical picture, one safety information form can be used to describe all the SAEs.

MESIs, regardless of seriousness, must be reported using both the AE form and the safety information form and an MESI form. The MESI form is a form tailored to collect specific information related to the individual MESI.

The AE form for a non-serious AE not fulfilling the MESI criteria should be signed when the event is resolved or at the end of the trial.

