### **Body weight**

The body weight endpoints will be analysed using a similar model as described for the primary endpoint except that the body weight at baseline will be included as a covariate and the analysis will be made on the original scale. Consequently, treatment means (LSMeans) and treatment differences will be presented with 95% CIs.

Body weight endpoints will be summarised using descriptive statistics and presented graphically.

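### The hypoglycaemia model leaves out each subject's pre-dose episode count, which is recorded from Visit 2: a modest loss of precision, not a bias or an inconsistency

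*SAP*

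**What the plan says.** SAP 2.4.1.2 (Analysis of hypoglycaemic episodes) fits a "negative binominal regression model with a log link function, and the logarithm of the exposure time as an offset". On adjustment it says: "The model will include treatment, stratum and sex as factors and age as a covariate". Protocol 17.4.1.2 has the same list. The model covers two outcome classes, severe or BG-confirmed symptomatic episodes and their nocturnal subset. Each is analysed for the treatment period, the observation period and the whole trial.

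An episode counts as treatment emergent "if the onset of the episode occurs on or after the first day of trial product administration", up to one day after last contact. Collection begins earlier. Protocol 8.4.2.7 says that qualifying glucose values "should be reported according to the instructions below throughout the trial from visit 2 to visit 89", and the footnote to Protocol 12.2 agrees: "With the exception of hyperglycaemic and hypoglycamic episodes for which reporting starts at V2". The flow chart puts Visit 2 at day -10 with a window of 4 days, and Visit 3 (randomisation and first dose) at day 0.

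The Protocol summary lists this count among its key secondary endpoints: "treatment emergent hypoglycaemic episodes according to the American Diabetes Association (ADA) and Novo Nordisk definitions from first dose of trial product to week 54". SAP 1.1.2.2 marks it for public disclosure. Protocol 8.2.7 also records "Number of severe hypoglycaemic episodes since diagnosis", which the model does not use. The list of changes in SAP section 3 does not mention this model, and no reason is given for leaving out a pre-dose count.

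**The concern.** A negative binomial model is chosen because subjects differ in their underlying episode rate. A count of the same kind of event before dosing measures that difference directly; stratum (peak C-peptide at Visit 2), sex and age are only proxies. Pre-dose episodes are not part of the outcome and cannot be affected by treatment, so the count is a proper baseline covariate. Leaving it out keeps explainable between-subject variation in the dispersion parameter, and the intervals for the rate ratios are somewhat wider than they need be. The trial was not sized for hypoglycaemia: the power calculation in SAP 2.1 concerns C-peptide only. A disclosed safety comparison with 76 subjects per arm could use precision that needs no new data.

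**Working it through.** **The plan's own figure.** There is none to reproduce. Neither document states a rate, dispersion, effect size or power for hypoglycaemia.

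**Inputs from the documents**
- 304 randomised 1:1:1:1 (Protocol 6.1 and 11): 304/4 = 76 per arm.
- 240 expected to reach the primary endpoint (Protocol 6.1): dropout 1 - 240/304 = 21%.
- Treatment period of 54 weeks.
- Pre-dose window: 10 - 4 = 6 to 10 + 4 = 14 days (flow chart).

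**Assumed inputs:** 2 to 20 modelled episodes per patient-year, frailty variance 1.5 (1 and 2 as alternatives), and correlation of 0, 0.5 or 0.8 between pre- and post-dose log frailties (1 as an upper limit).

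**Step 1: how much the count can carry.** Expected pre-dose count = rate x days / 365.25. With 10 days this is 2 x 10/365.25 = 0.055 at 2 per year and 20 x 10/365.25 = 0.55 at 20 per year. At 2 per year about 95% of subjects have a count of zero.

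**Step 2: gain in precision.** Negative binomial models were fitted to 40,000 simulated subjects with and without the count, and the standard errors were rescaled to 76 against 76. Reduction in variance = 1 - (SE with / SE without)². For a 10-day window and frailty variance 1.5:

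| Episodes per year | Correlation 0 | Correlation 0.5 | Correlation 0.8 |
|---|---|---|---|
| 2 | 0% | 0.5% | 2.5% |
| 5 | 0% | 2% | 7% |
| 10 | 0% | 3% | 10% |
| 20 | 0% | 6% | 16% |

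Letting the window vary over 6 to 14 days and including the 21% dropout gives about 0.5 to 6% at correlation 0.5, 1 to 17% at 0.8, and no change at zero.

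**Step 3: sensitivity to the assumptions.** With frailty variance 1 or 2, a 10-day window and correlation 0.5, the reduction is 0.5 to 0.9% at 2 per year, 1.6 to 2.5% at 5, 3.3 to 3.9% at 10 and 5.6 to 6.6% at 20. If each subject's rate were perfectly stable (correlation 1), it would be 3-5%, 8-12%, 15-21% and 25-31%. These fits also carried an indicator for a zero count.

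**Step 4: effect on the interval.** Interval width goes with the square root of the variance. A 6% reduction narrows it by 1 - √0.94 = 3.0%, and a 17% reduction by 1 - √0.83 = 8.9%.

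**Step 5: form of the covariate.** Dividing (count + 0.5) by run-in days adds noise among zero-count subjects. Between a 6-day and a 14-day window their covariate would differ by ln(14/6) = 0.85, with no episode in either. The step from zero to one episode is only ln(1.5/0.5) = 1.10. In simulation the division roughly halved the small gain at 2 per year.

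**The case against.** The strongest case is that this is a preference for one more covariate. The endpoint is a count from first dose. The endpoints that the SAP adjusts for their own baseline, such as weight ("except that the body weight at baseline will be included as a covariate"), are changes or ratios to baseline. Another modelled endpoint that is not a change, before-breakfast SMPG, also has no baseline term. A reader might infer from the contrast that the SAP is inconsistent, or that the rate ratio is biased. The documents support neither: the SAP's practice is coherent, and randomisation with a log link keeps the unadjusted ratio valid. That part of the objection stands in full.

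High correlation is also doubtful. Between the pre-dose window and most of follow-up come the insulin reductions at liraglutide or placebo initiation and escalation (Protocol 5.3.3), weekly titration (Appendix A) and possible pausing of insulin. The meter and diary are first issued at Visit 2, so the window is a learning period too. The observation period starts about a year later.

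Nor can a count be assumed for every randomised subject. Under Protocol 8.4.2.7, non-severe episodes with no form completed within 7 days are not added later, and gaps are generally not queried. An empty diary can therefore look like zero episodes.

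A reader might also infer gains of a third or more. Such figures (up to 34% at 20 per year and correlation 0.8) describe the sandwich variance, or (38%) a perfectly stable rate of 20 per year with a 14-day window. Nothing in the documents points to those conditions.

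What the objection does not remove is that the data are already collected, and that the simulations show no loss when the count carries no information.

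**Conclusion.** The point holds as a small, optional gain in efficiency. A true pre-treatment count is available and unused. Under the assumptions above it would reduce the model-based variance by about 0.5 to 6% at correlation 0.5 and 1 to 17% at 0.8, so intervals would be at most about 3% and 9% narrower respectively. At zero correlation nothing changes, and for rare classes such as nocturnal episodes the gain is near nil. The direction needs only a positive correlation between a subject's pre- and post-dose rates. The size rests wholly on assumed rates, frailty variance and correlation. The planned analysis is valid as it stands.

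**What to change.** Before unblinding at the interim database lock (SAP 2.4.2), amend SAP 2.4.1.2 as follows:
- Add log(pre-dose episode count + 0.5), counted from Visit 2 to the day before first dose, to the treatment-period negative binomial models. Use the same term for the other two periods.
- Do not divide the offset count by run-in days. If window length matters, enter log(run-in days) as a separate term.
- To reduce sparsity, the count may include all recorded episodes with plasma glucose at or below 3.9 mmol/l or with symptoms. If this broader count were four times as frequent and shared the same frailty (both assumptions), the variance would fall by 2.5 to 12% at correlation 0.5 and 8 to 31% at 0.8, for 2 to 20 modelled episodes per year.
- State how subjects without pre-dose diary entries are handled, for example by a missing indicator and not by a zero.
- Keep the present model as a sensitivity analysis.

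The cost is one more model term and a missing-diary rule, with no new data. Little or nothing is gained if pre- and post-dose rates are weakly correlated. If the sponsor prefers the present model, a sentence giving the reason would settle the point.
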